### **4.3. Life Style Guidelines**

During the study female patients of childbearing potential must take precautions to prevent pregnancy since the effects on the foetus are unknown. Male patients with partners of childbearing potential must take precautions to prevent pregnancy of the partner since the effects of these drugs on sperm are unknown. These restrictions should remain in force for 6 months from the last dose of investigational agent. Drug interaction studies with oral contraceptives have not been performed, so barrier methods of contraception or abstinence should be considered. Adequate contraception should be discussed with the physician before the treatment start and should be in agreement with local laws.

## **5. Study Procedures**

### **5.1. Allocation to Treatment**

Participants will be identified from Oncology clinics at Imperial College Healthcare NHS Trust by a member of the clinical research team who has been certified in Good Clinical Practice. Patients will receive detailed information sheets (see appendix) and offered a link to the study website where they can review the study and gain further information.

### **5.2 Randomisation**

Patients will be randomised in a ratio of 2:1 to Axitinib monotherapy or placebo. This will be performed centrally by an independent system (Imperial 'Inform' system 2011) to maintain blinding. Anonymised randomisation details will be kept off site and not disclosed to the study team until follow up is completed.

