In colorectal cancer (CRC), the lack of classical responses has prompted the exploration of VEGF inhibitors such as Sunitinib in monotherapy. The clinical evidence means that we should be exploring how to use these drugs in novel ways. Indeed, the efficacy of single agent Sunitinib in chemorefractory CRC has been investigated in a Phase 2 study (A6181003), where there appeared to be stabilising activity and additionally a small subset of patients went on to respond. In this study, 84 patients were enrolled, 43 with prior Bevacizumab and 41 without prior Bevacizumab treatment. 82 patients were actually treated with Sunitinib and comprised the intention-to-treat population (1 patient in each cohort discontinued the study before receiving treatment). Overall, 67 (82%) patients discontinued the study due to disease progression, 8 (10%) due to adverse events, 1 (1%) was lost to follow-up, and 5 (6%) withdrew consent. One patient completed the study (1 year of therapy). In the analysis of the primary endpoint – overall response rate (ORR) - only 1 patient with prior Bevacizumab therapy had a confirmed partial response; twenty-four patients (29%; 10 [24%] with and 14 [35%] without prior Bevacizumab) had a best response of stable disease – among those, 2 (4.8%) with and 11 (27.5%) without prior Bevacizumab experienced stable disease for  $\geq 22$  weeks. Although Sunitinib failed to show significant classical responses in this population of heavily pretreated patients, an encouraging survival of 10 months was observed amongst Bevacizumab-naïve patients. This survival rate along with Sunitinib's mechanism of action and acceptable safety profile suggest that further investigation of Axitinib or similar drugs is warranted. Indeed, although cross trial comparisons are difficult: 10 months is as good as the Bevacizumab monotherapy arm in the second-line Bevacizumab naive E3200 study [ENREF 5](#).

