### 3. Study Design

A Phase II, double-blind, 2 arm pilot randomised placebo controlled trial. 50 patients will be sequentially randomised 2:1 to Axitinib or placebo.

Inclusion criteria: Chemorefractory third-line metastatic CRC with US-assessable liver or other abdominal metastases that can have a baseline DCEUS baseline measurement.

Treatment arm: Axitinib monotherapy started in all patients at 5mg bd, and increased fortnightly by a dose level (See Table 4) as tolerated to a maximum dose of 10mg bd.

Control arm: Placebo (blinded) randomised 2:1 to Axitinib : placebo

Follow up: Outpatient monitoring at 2 weeks and 4 weeks post first dose then 4 weekly thereafter with RECIST restaging every 8 weeks. CEHPI at baseline, 2 weeks and 8 weeks for assessment of differential blood supply (CEHPI) with an optional visit at 48-72 hours post first dose. VEGF-PK samples at Day 15 & Day 28 and at 8 weeks and RECIST progression. At 8 weeks, after tumour CT RECIST assessments, conventional responders (CR/PR/SD) continue monotherapy. In non-responders (PD), monotherapy can be continued if patient chooses to continue and if tolerated. CT response assessments continue at 8 weekly intervals in all patients, with parallel 8 weekly DCE-US. CEHPI at baseline, optionally at 47-72 hours, 2 weeks, 8 weeks and at progression of disease.

[figure not shown]

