## 6. Study Procedures

### 6.1 Screening

Demographic data, clinical history, response to previous treatments, functional status, imaging and histology results to date will be ascertained at baseline on a standard case report form (CRF). Patients will be eligible irrespective of k-ras mutation status.

The following screening procedures will be performed within up to 28 days prior to the start of treatment on study, unless otherwise stated:

- Patient signature on informed consent form (up to 28 days prior to treatment)
- Medical history including confirmation of histological diagnosis, history of other concomitant illnesses
- Demographics (including age, sex, and race)
- Physical examination including examination of major body systems, ECOG performance status, body weight, height (screening only), and vital signs (temperature, blood pressure, heart rate)
- Haematology performed within 7 days from treatment start
- Chemistry, CEA and CA19.9 performed within 7 days from treatment start
- Coagulation (APTT & INR) performed within 7 days from treatment start
- Thyroid Function Tests (free T3, free T4 and TSH)
- Pregnancy test (urine), if applicable, performed within 7 days from treatment
- Urinalysis by dipstick
- 12-Lead electrocardiogram
- Endoscopy or upper GI imaging, to exclude patients with suspected oesophageal varices and/or gastroduodenal ulcer.
- Assessment of concomitant medications and treatments
- Assessment of ongoing symptoms/events (serious adverse events must be recorded from time of signed consent)
- Study randomisation upon completion of all screening assessments
- Baseline (screening) tumour assessments require CT/MRI (no chest x-ray) of the chest and abdomen at the minimum. If the interval between any of the baseline tumour assessments and randomisation is >28 days, the baseline tumour imaging will be repeated.

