## 9.2 Statistical analysis plan

The primary analysis will be on PFS by Kaplan-Meier of patients who manage to complete at least 2 weeks of Axitinib therapy (versus Placebo).

For the secondary analyses:-

A stratified log-rank test (1-sided,  $p=0.025$ ) will be used to compare PFS between CEHPI responders and non-responders. The median event time and 2-sided 95% CI for the median will be provided. The hazard ratio and its 95% CI will be also estimated.

The optimum CEHPI cut-point for determining response will be confirmed using the percentage change in CEHPI against RECIST response using a receiver operator characteristic curve. Test statistics including sensitivity, specificity, positive predictive value, negative predictive value, odds of disease progression and area under the curve will be calculated for 2 week CEHPI reduction in predicting disease progression.

A similar analysis will be performed with diastolic blood pressure.

Overall survival is defined as the time from date of randomisation to date of death due to any cause. For patients not expiring, their survival times will be censored at the last date they are known to be alive. Patients lacking data beyond the day of randomisation will have their survival times censored at the date of randomisation with duration of 1 day. Overall survival will be summarised using Kaplan-Meier methods and displayed graphically where appropriate. A stratified log-rank test (1-sided,  $p=0.025$ ) will be used to compare OS between CEHPI responders and non-responders. The median event time and 2-sided 95% CI for the median will be provided. The hazard ratio and its 95% CI will be also estimated.

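### Prior bevacizumab is left out of the randomisation and the PFS comparison, although the protocol's own cited study suggests it matters; stratifying by it is a cheap, minor improvement

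*Combined protocol and SAP*

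**What the plan says.** - **Randomisation.** Section 3 states that "50 patients will be sequentially randomised 2:1 to Axitinib or placebo". Section 5.2 repeats that "Patients will be randomised in a ratio of 2:1 to Axitinib monotherapy or placebo" and adds that this is done centrally by an independent system. Neither names a stratification factor, a block scheme or minimisation.
- **Primary analysis.** Section 9.2: "The primary analysis will be on PFS by Kaplan-Meier of patients who manage to complete at least 2 weeks of Axitinib therapy (versus Placebo"). It names no test, stratum or covariate for this comparison.
- **Stratified tests.** Section 9.2 does plan a stratified log-rank test, but it "will be used to compare PFS between CEHPI responders and non-responders", and a second one does the same for OS. The strata are not named.
- **Eligibility.** Sections 4.1 and 4.2 require earlier oxaliplatin, irinotecan and fluoropyrimidine. They do not mention bevacizumab, so pretreated and naive patients both enter.
- **Cited evidence.** Section 1.2, on single-agent sunitinib in chemorefractory disease, reports that "2 (4.8%) with and 11 (27.5%) without prior Bevacizumab experienced stable disease for" 22 weeks or longer.
- **Baseline data.** Section 6.1 lists "Demographic data, clinical history, response to previous treatments, functional status" among the items recorded, so treatment history is already being taken.
- **Use of the result.** Under Section 9.1, an observed PFS gain above 6 weeks leads to a funding application for phase III. The same section says that 50 patients do not give conventional power.

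**The concern.** The protocol reports a large contrast by prior bevacizumab in its background. Section 9.1 then pools both groups (13 patients with long stable disease) to set expectations, and the factor appears in neither the randomisation nor the arm comparison. With about 33 v 17 patients, a binary baseline factor can fall unevenly by chance. If it is prognostic, part of the observed PFS difference then reflects who had received bevacizumab.

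The trial is run once and its observed difference feeds the go rule and the phase III sample size. After an imbalanced draw, no prespecified analysis would be available to correct the result. The CEHPI responder comparison, listed as co-primary in Section 2.2, is not randomised, so which baseline factors it is stratified by matters there too.

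**Working it through.** **1. The cited figures.** Section 1.2 gives 43 and 41 enrolled, one in each cohort untreated, so 42 and 40 treated.
- Stable disease for at least 22 weeks: 2/42 = 4.8% and 11/40 = 27.5%. Both reproduce, and 2 + 11 = 13 agrees with Section 9.1. Fisher two-sided p = 0.006.
- Any stable disease: 10/42 = 24% and 14/40 = 35%, p = 0.33.

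**2. Implied hazard ratio.** Assume exponential PFS and treat the 22-week rates as PFS rates.
- Pretreated: ln(42/2)/22 = 0.1384 per week, median ln 2/0.1384 = 5.0 weeks.
- Naive: ln(40/11)/22 = 0.0587 per week, median 11.8 weeks.
- Ratio 0.1384/0.0587 = 2.36 (delta-method 95% CI about 1.3 to 4.3).
- Counting the one partial response in the pretreated cohort as long control: 3/42, ln(42/3)/22 = 0.1200, ratio 2.04 (about 1.2 to 3.6).

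**3. How often the arms are imbalanced.** The standard deviation of the arm difference in the pretreated share is √[p(1−p)(1/33 + 1/17)], which is 0.149 at p = 0.5. Exact binomial probability of a difference of 20 points or more:

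| Pretreated share (assumed) | Probability |
|---|---|
| 10% | 3% |
| 20% | 10% |
| 30% | 13% |
| 50% | 16% |

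Shares of 70% and 90% mirror 30% and 10%. About half of these imbalances favour axitinib. A difference of 30 points or more has probability 4.6% at p = 0.5.

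**4. What an imbalance does to the medians, with no drug effect.** Take half of all patients pretreated and a 20-point gap: 43.2% pretreated on axitinib and 63.2% on placebo. The mixture medians are 7.95 and 6.67 weeks, a shift of 1.28 weeks (1.15 with the ratio of 2.04). A 30-point gap shifts the difference by 1.9 weeks. Complete separation, all naive v all pretreated, gives 11.8 − 5.0 = 6.8 weeks.

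**5. The 6-week go rule, with no drug effect.** Simulated with 33 v 17 patients, half pretreated, the factor acting equally in both arms and everyone progressing. Imbalanced means by 20 points or more. Section 9.1 gives a control PFS of 6 to 8 weeks.

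| Setting | Favours axitinib | Balanced | Favours placebo | Overall, unstratified | Overall, balanced by design |
|---|---|---|---|---|---|
| 8-week scans, mixture median 7 weeks, factor HR 2.0–2.4 | 30–33% | 19% | 8–10% | 19.4% (HR 2.36) | 20.3% (HR 2.36) |
| 8-week scans, mixture median 7.5 weeks, HR 2.36 | 39% | 22% | 10% | 23.3% | 22.8% |
| Continuous PFS, mixture median 7.5 weeks, HR 2.36 | 7.8% | 2.6% | 0.6% | 3.1% | 2.5% |

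The overall rate hardly moves because the two directions nearly cancel: 0.08 × 33% + 0.08 × 9% + 0.84 × 19% ≈ 19.3%. At a true hazard ratio of 0.5 on the scan grid (mixture median 7.5 weeks), the go probability is 72.8% unstratified and 72.4% stratified.

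**6. Log-rank power at a true hazard ratio of 0.5, one-sided 0.025.** With a factor HR of 2.36, one set of runs gives 53% unadjusted, 59% with a stratified test, and 62% with stratified randomisation as well. Another, on the scan grid, gives 50% and 55%. Over factor HRs of 2.0 to 2.4 the gain is about 3 to 9 points. At a factor HR of 1.5 it is about 1 point or less.

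These calculations ignore the few patients dropped by the 2-week completion rule.

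**The case against.** The strongest objection is to the evidence. The study is of sunitinib, has no control arm as described, and rests on 2 and 11 patients in non-randomised cohorts. It cannot tell a prognostic factor (acting on placebo patients too) from a predictive one (resistance to a second VEGF agent). If the factor is only predictive, imbalance cannot create a false signal when the drug does nothing. The difference in any stable disease is much smaller, and a factor HR of 1.5, at which the power gain vanishes, lies inside both intervals in step 2. All of this stands.

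A reader might infer that the cited data show prior bevacizumab changing disease control, and that chance imbalance can by itself make or hide the PFS signal. The documents do not support that. A 20-point imbalance is worth about 1.3 weeks against a 6-week threshold. Most of the false-go rate comes from 17 placebo patients and 8-weekly scans, and stratifying does not reduce it.

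A reader might also infer that prior bevacizumab confounds the CEHPI comparison by a known amount. The documents give no CEHPI response rate by prior bevacizumab, and Section 9.2 already plans stratified tests there. The gap is that the strata are unnamed.

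Finally, an unstratified, unadjusted comparison is valid, and Section 9.1 claims no power. That is correct. It lowers the priority but does not answer how an imbalanced result would be read.

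**Conclusion.** The omission is real: neither the randomisation nor the arm comparison of PFS uses prior bevacizumab, and the protocol's own background gives a reason to use it. The consequence is modest. If the factor is prognostic with HR about 2 to 2.4 and about half the patients are pretreated, roughly one trial in six has an imbalance of 20 points or more, enough to tip a borderline go decision either way. With 10 to 30% pretreated it is 3 to 13%. The overall false-go rate is essentially unchanged by stratifying. The benefit is a single trial that can be interpreted, plus a small gain in power that disappears if the factor is weak.

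The share of pretreated patients is not in the documents. Section 14 describes a population whose disease progressed on, or who could not tolerate, a single earlier anti-angiogenic treatment; the eligibility criteria contain no such requirement. If all patients had received such therapy, the point would largely vanish. This is a minor improvement, held with medium confidence.

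**What to change.** - **Data collection (Section 6.1):** record prior bevacizumab or other anti-VEGF therapy as an explicit yes/no field.
- **Section 5.2:** stratify the central 2:1 randomisation by that field. If this is not possible, at least prespecify the factor in the analysis.
- **Section 9.2, arm comparison:** specify a log-rank test and a Cox model for PFS and OS, both stratified by the factor, and report its distribution by arm.
- **Section 9.2, CEHPI comparison:** name the factor as the stratum of the stratified log-rank tests, whose strata are now undefined.
- **Section 14:** reconcile the population described there with Sections 4.1 and 4.2.

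One factor is enough for 50 patients; the documents give no comparable outcome data for others such as ECOG status. The cost is one field in the CRF and randomisation system and a few lines of text, with no extra patients or procedures.

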### **5.3 Blinding**

Patients, sonographers and clinicians will be blinded to therapy. Pharmacy will have an anonymised coding ticket system for dispensing drug/ placebo once randomisation is complete. Unblinding will only occur at the discretion of the data monitoring committee or the investigators in an emergency situation (including out-of-hours), primarily for safety reasons throughout the duration of the trial.

### **5.4 Drug Supplies (Axitinib and Placebo)**

Axitinib and placebo will be supplied for the study by the Global Supply Chain, Pfizer Global Research and Development. Clinical Trial Material (CTM) will be shipped to the study sites with instructions on how to confirm drug receipt.

### **5.5 Formulation and Packaging**

Axitinib and placebo will be supplied as 1 mg and 5 mg film-coated tablets for oral administration in light-protecting bottles.

### **5.6 Preparation and Dispensing**

Axitinib and placebo tablets will be dispensed in opaque plastic bottles to protect from light. Axitinib is a hazardous drug (due to possible reproductive toxicity), and should be handled according to the recommended procedures described in the current edition of the American Society of Hospital Pharmacists (ASHP), Technical Assistance Bulletin on Handling Cytotoxic and Hazardous Drugs, American Hospital Formulary Service (AHFS) Drug Information (1999) and its references. Procedures described in each institution's pharmacy or hospital standard operating procedure manual should be followed when handling hazardous drugs.

## 5.7 Administration

Study treatment must begin within 7 days of randomization

## 5.8 Dosing

The recommended starting dose of Axitinib is 5 mg bd taken orally with food. Dose adjustments, including dose increase or dose reduction should be based on adverse events experienced by the individual patient. Axitinib should be taken beginning on Day 1 of the study. Doses should be taken approximately 12 hours apart continuous dosing.

Patients will be instructed to take their doses at approximately the same times each day. Patients will be instructed that if they vomit after taking a dose, that they must not take an extra dose, but instead resume subsequent doses as prescribed. Any missed dose may be taken late up to 3 hours before the next scheduled dose, otherwise, it should be skipped. If doses are missed or vomited, this must be indicated in the source documents and CRFs. Study treatment will be administered in cycles of 4 weeks in duration.

Patients who tolerate Axitinib with no adverse events related to study drug above CTCAE Grade 2 for consecutive 2-week period should have their dose increased by one dose level (see Table 4) to a maximum of 10 mg bd (unless the patient's blood pressure is >150/90 mm Hg or the patient is receiving antihypertensive medication). Patients experiencing drug reaction greater than CTCAE Grade 2 should undergo dose modification. For the patients receiving Axitinib, concomitant medications that are known to substantially inhibit the enzyme, CYP3A4, should be avoided as much as medically possible. The clinical judgment, taking into account all of these parameters, of the treating physician should be exercised in titrating Axitinib dose.

Available Axitinib Dose Levels	Dose
+2	10 mg BD
+1	7 mg BD
0 (Starting Dose)	5 mg BD
-1	3 mg BD
-2	2 mg BD

Table 4: Axitinib dose modification table

## 5.9 Dose Interruption and Reduction

Adverse events and other symptoms will be graded according to the current Common Terminology for Adverse Events version 4.03.

## 5.10 Management of Axitinib-Related Adverse Events

This section contains management of adverse events except hypertension and proteinuria which are discussed in subsequent sections. Patients developing Axitinib related CTCAE Grade 1 or 2 adverse events may have their dose continued at the same dose level (See Table 4). Patients removed from treatment for intolerable toxicity should still be followed with regular tumour assessments until disease progression or start of new treatment, and

Related Adverse Events	INTERVENTION
Grade 1	Continue at same dose level
Grade 2	Continue at same dose level
Grade 3 non-haematologic treatment-related toxicity*	Decrease dose to one lower dose level
Grade 4 non-hematologic treatment-related toxicity or Grade 4 hematologic toxicity**	Interrupt dosing; re-start at one lower dose level as soon as improvement to CTCAE Grade $\leq 2$ . If patient requires dose reduction below 2 mg BD, contact sponsor for discussion prior to implementation.

for survival thereafter.

**Table 5: Adverse event action plan**

\* Patients who develop Grade 3 non-haematologic toxicities that are controlled with symptomatic medications or Grade 3 asymptomatic biochemistry laboratory abnormalities may be continued at the same dose level at the discretion of the investigator.

\*\* Patients who develop Grade 4 lymphopenia or Grade 4 asymptomatic biochemistry laboratory abnormality may continue study treatment without interruption.

## 5.11 Axitinib/Placebo Dose Reduction for Hypertension

Patients treated with Axitinib/placebo will be issued blood pressure cuffs (provided by Pfizer Inc) for home monitoring and instructed to measure their blood pressure (BP) twice daily, prior to taking each dose. All blood pressure measurements will be recorded in a diary and brought to the nurse or study coordinator at each clinic visit. Patients should be instructed by the study staff to contact their physician for guidance if their systolic blood pressure rises above 140 mm Hg, diastolic blood pressure rises above 90 mm Hg, or if they develop symptoms perceived to be related to elevated BP (eg, headache, visual disturbance). See below for dose modifications for hypertension. A different blood pressure threshold for contacting physician may be used according to the physician's clinical judgment. See below for dose modifications for hypertension.

New or additional antihypertensive therapy (see Section 5.4, Concomitant Medication(s) for guidance) should be started if 2 BP readings, preferably taken in the clinic and separated by at least 1 hour, show the following: 2 systolic BP readings greater than 140 or 2 dBP readings greater than 90 mm Hg. Alternately, the dose of existing antihypertensive medication(s) may be increased. Investigator may use clinical judgment to start new or additional antihypertensive therapy at a lower blood pressure threshold. If the patient is already on maximal antihypertensive treatment, the Axitinib dose should be reduced by 1 dose level (see Table 4).

Patients who have 2 systolic BP readings, separated by at least 1 hour, greater than 160 mm Hg, or 2 dBP readings, separated by at least 1 hour, greater than 105 mm Hg, will have treatment with Axitinib/placebo held. (Note: if Axitinib/placebo is held, patients receiving antihypertensive medications should monitor closely for hypotension and restart Axitinib/placebo at one lower dose level (see Table 4) as soon as BP is <140/90 mm Hg. The plasma half-life of Axitinib is 2 – 4 hours and BP usually decreases within 1-2 days following dose interruption.)

Patients removed from treatment for intolerable toxicity should still be followed with regular tumour assessments until disease progression or start of new treatment, and for survival thereafter.

Degree of Blood Pressure Elevation			
Systolic Pressure	OR	Diastolic Pressure	Management
2 BP readings separated by at least 1 hour show systolic pressure >150 mm Hg		2 BP readings separated by at least 1 hour show diastolic pressure >100 mm Hg	If not on maximal antihypertensive treatment, institute new or additional antihypertensive medication and maintain dose of Axitinib.  If on maximal antihypertensive treatment, reduce Axitinib to one lower dose level.
2 BP readings separated by at least 1 hour show systolic pressure >160 mm Hg	OR	2 BP readings separated by at least 1 hour show diastolic pressure >105 mm Hg	Stop Axitinib; adjust antihypertensive medication; as soon as BP is less than 150/100 mm Hg, restart Axitinib at one lower dose level.
Recurrent hypertension following previous dose reduction (2 BP readings separated by at least 1 hour show systolic pressure >150 mm Hg)	OR	Recurrent dBP >100 mm Hg (2 BP readings separated by at least 1 hour) following previous dose reduction	Repeat Axitinib dose reduction by one lower dose level. If a patient requires dose reduction below 2 mg BD, contact Sponsor for discussion

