#### Trial Treatment

Axitinib or placebo will be administered, twice daily (bd) on a continuous daily dosing schedule, to patients randomised to Arm A or Arm B, respectively. The starting dose will be 5mg BD which will be increased fortnightly by a dose level (See Table 4) as tolerated to a maximum dose of 10mg bd. Doses should be taken with food as close to 12 hours apart as possible and at approximately the same times each day on a continuous schedule. Patients who tolerate Axitinib/placebo with no adverse events related to Axitinib/placebo above CTCAE Grade 2 for a consecutive 2-week period should have their dose increased by one dose level unless BP is >150/90 mm Hg. [The clinical judgment of the treating physician should be exercised when titrating Axitinib/placebo dose. In cases where it is not obvious whether Axitinib is a contributor to adverse event(s), dose titration will remain at the investigator's discretion.

The study treatment may be permanently discontinued upon progression of disease, occurrence of unacceptable toxicity, withdrawal of patient consent, or other withdrawal criterion is met. However, patients who have progressive disease (PD) but have experienced clinical benefit from Axitinib or placebo treatment will be eligible for continued treatment

provided that the treating physician has assessed the risk/benefit of taking such an approach and no alternative treatment is available.

Patients who require different systemic cancer treatment from what they were assigned at randomization must be withdrawn from the study and followed as described below. After discontinuation of study treatment and the mandated 28-day follow-up period, patients will continue to be followed in order to collect information on further anti-tumour therapy and survival.

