## **AXMUS-C Principal Investigator**

### **Trial summary**

AXMUS-C (AXitinib Monotherapy Ultrasound in Colorectal cancer) is a double blind, randomised, 2 arm, phase II trial to identify if responders to Axitinib have greater overall survival than Axitinib non-responders and the placebo groups. Both arms commence with 8 weeks of either Axitinib monotherapy or placebo. Response will be judged using an imaging biomarker called the contrast enhanced ultrasound hepatic perfusion index.

Axitinib is a tyrosine kinase inhibitor against vascular endothelial growth factor receptors. It is administered orally at an initial dose of 3mg b.d. which can be titrated upwards to a maximum dose of 10mg b.d..

50 patients with metastatic colorectal cancer who are fit for Axitinib chemotherapy will be randomised at the start of chemotherapy to receive **initially**:

**Arm 1: Daily Axitinib** treatment for 8 weeks (2/3rds of patients)

*OR*

**Arm 2: Daily placebo** treatment for 8 weeks (1/3rd of patients)

[figure not shown]
The primary outcome measure will be overall survival in the patients whose liver blood flow measured by a special ultrasound test is changed by Axitinib. Secondary outcome measures include progression-free survival, overall response rate and toxicity.

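### Section 5.11 contradicts its own Table 6 on when to treat, reduce and restart for raised blood pressure, and Sections 5.8 and 3 disagree on up-titration in patients on antihypertensives.

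*Combined protocol and SAP*

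**What the plan says.** **Treating raised pressure.** The running text of Section 5.11 calls for new or additional antihypertensive treatment at "2 systolic BP readings greater than 140 or 2 dBP readings greater than 90 mm Hg". In the same paragraph, a patient already on maximal antihypertensives drops one dose level. The first row of Table 6 triggers the same two actions when "2 BP readings separated by at least 1 hour show systolic pressure >150 mm Hg", or when two diastolic readings exceed 100.

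**Restarting after a hold.** Text and table agree on when to hold (two readings above 160 systolic or 105 diastolic). They differ on the restart: the text says "as soon as BP is <140/90 mm Hg", the table says "as soon as BP is less than 150/100 mm Hg, restart Axitinib at one lower dose level".

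**Up-titration.** Section 5.8 withholds the increase if pressure is above 150/90 "or the patient is receiving antihypertensive medication". The Trial Treatment part of Section 3 says that patients who tolerate the drug "should have their dose increased by one dose level unless BP is >150/90 mm Hg", with no mention of antihypertensive use. The Trial Summary also omits that bar, but its sentence refers the reader to 5.8.

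**Lesser discrepancies.** Section 5.8 states: "The recommended starting dose of Axitinib is 5 mg bd taken orally with food". The trial summary placed among the appendices states: "It is administered orally at an initial dose of 3mg b.d". Exclusion criterion 16 sets contraception at up to 3 months after stopping study drug; Section 4.3 sets 6 months from the last dose.

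**The concern.** These are operating instructions for a toxicity the protocol expects to be common. Where two current passages give different actions for the same readings, a site can comply with one only by departing from the other, and a monitor cannot say what counts as a deviation. Nothing states whether the text or the table takes precedence.

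There is a statistical cost as well as a safety one. Holds, reductions and escalations determine dose received. PK is sampled at day 15, day 28 and 8 weeks, and CEHPI is measured at 2 and 8 weeks; the plan intends to correlate the two. If the rule in use varies by clinician or by visit, part of the variation in exposure reflects which page was read, not tolerance or biology, and in a 50-patient pilot it could not be separated afterwards.

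**Working it through.** No sample-size or error-rate figure is involved, so the check sets the rules side by side and applies them to specific patients.

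| Decision | One place | Other place |
|---|---|---|
| Start or add antihypertensive | 5.11 text: >140 or >90 | Table 6: >150 or >100 |
| Reduce one level if on maximal therapy | 5.11 text: >140 or >90 | Table 6: >150 or >100 |
| Hold | 5.11 text: >160 or >105 | Table 6: the same |
| Restart after hold | 5.11 text: <140/90 | Table 6: <150/100 |
| Up-titration | 5.8: not if >150/90 or on an antihypertensive | Section 3: not if >150/90 |

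The start and reduction rules diverge when systolic is above 140 up to 150, or diastolic above 90 up to 100, with neither value over the Table 6 limit. The row of Table 6 for recurrent hypertension also uses 150 and 100, so the higher pair is not a single slip.

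Applied to patients:

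1. *Held, pressure now 145/95.* Table 6 restarts at one lower level, since 145 < 150 and 95 < 100. The text keeps holding, since 145 is not below 140 and 95 is not below 90.
2. *145/95 on two readings, on maximal therapy.* The text reduces one level. No row of Table 6 is triggered.
3. *135/85 on an antihypertensive, no related event above Grade 2 for two weeks.* Section 3 escalates; 5.8 does not.
4. *145/88 on two readings, not on an antihypertensive, otherwise tolerating.* The 5.11 text starts an antihypertensive because 145 > 140, and 5.8 then blocks escalation. Under Table 6 nothing is triggered, and because pressure is not above 150/90, both 5.8 and Section 3 allow the increase. The two conflicts therefore compound.

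Discretion clauses were checked as a possible resolution. Section 5.11 lets the investigator start antihypertensives at a lower pressure than its own limit; nothing there permits waiting for the higher limit in Table 6. The freedom to vary a threshold for contacting the physician concerns contact only. Clinical judgement is allowed in titration, but no passage says which default it departs from. No clause addresses the two restart values.

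The lesser items: 5 mg bd is level 0 in Table 4 and 3 mg bd is level -1, one level apart. The contraception periods differ by 6 - 3 = 3 months.

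**The case against.** Several points on the other side are sound.

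- For a patient not on maximal therapy, Table 6 does not forbid treatment between the two limits. A site reading both could treat at the lower limit without breaching the table. The restart values cannot be reconciled this way: each rule says to restart as soon as its own limit is met.
- The Trial Summary defers to 5.8, so the unreferenced up-titration conflict is Section 3 against 5.8.
- All the operative dosing passages give 5 mg bd. A reader might infer that patients could actually be started on the other dose, or that an outside doctor would be misled. The documents do not show either: the 3 mg bd figure stands only in an appended summary, and its role as a letter to the general practitioner is only suggested by the contents list.
- Exclusion 16 tests willingness at entry and 4.3 governs conduct, so meeting the longer period also meets the shorter. Neither contraception figure touches an efficacy or PK variable.

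A reader might also infer that the conflict decides who counts as having diastolic pressure above 90, a secondary endpoint. It does not do so directly: a patient in the disputed diastolic band, above 90 up to 100, has already crossed that line. Any effect is indirect, through treatment triggered by systolic pressure alone or through later dose changes. Nor can the up-titration conflict reach the 2-week CEHPI of the co-primary endpoint, since escalation needs two tolerated weeks first.

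**Conclusion.** The point stands for the two 5.11 conflicts (treatment or reduction trigger, and restart pressure) and for Section 5.8 against Section 3. These are contradictions in current text that no other passage resolves, and they should be settled before anyone is dosed further under this protocol. The blood-pressure conflict lies inside one section, between text and table. The starting-dose and contraception discrepancies are real but minor.

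The size cannot be stated as a count. A reader might take 56/128 = 44% any-grade hypertension (22/128 = 17% grade 3/4) from the single-agent column of Table 1, multiply by 50 x 2/3 = about 33 Axitinib patients, and conclude that 0.44 x 33 = about 14 to 15 will be affected. That does not follow. Any-grade hypertension is not the same as two readings inside the disputed band, or as a hold followed by partial recovery; placebo patients follow the same rules; and the base is unclear, since Section 1.4 introduces 364 subjects while the column shows 128. The figure supports only the statement that the toxicity is common.

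The effect on PK and later CEHPI is a possibility that follows from dose being changed; its direction and amount are not derivable from the documents.

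**What to change.** The sponsor and clinical lead should reconcile each pair of passages in one amendment: the start and reduction thresholds and the restart threshold, stated identically in the 5.11 text and Table 6; and the up-titration condition, stated identically in the Trial Summary, Section 3 and Section 5.8. The same amendment should reconcile the starting dose in the appended summary with the dosing sections, and the two contraception periods. Which threshold, dose or duration stands is their decision.

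For patients already treated, record at each hold, restart, reduction and titration decision which of the conflicting rules was applied. Recording the protocol version in force would not help, because both rules sit in the same version.

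The cost is wording changes in one amendment, re-issue of the appended summary if it has been distributed, and a retrospective note in the case report form for affected decisions. Sample size, visits and analyses do not change.
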